6.4.4.1 Pneumonitis

Table 6-13 Management of Pneumonitis

(refer to [Table 6-5](#) and [Table 6-6](#) for dose reduction guide)

Worst Grade Pneumonitis	Required Investigations	Management of Pneumonitis	Dose Adjustment
Grade 1 Asymptomatic radiographic findings only	CT scans with lung windows Repeat at least every 8-12 weeks until return to within normal limits.	No specific therapy is required Consider flovent until resolution	Administer 100% of study treatment dose.
Grade 2 Symptomatic, not interfering with ADL	CT scan with lung windows. Consider pulmonary function testing includes: spirometry, DLCO, and room air O ₂ Saturation at rest Repeat at least every 8-12 weeks until return to within normal limits. Consider a bronchoscopy with biopsy and / or BAL	Symptomatic only. Consider flovent and corticosteroids if symptoms are troublesome.	Reduce study treatment by one level until recovery to ≤Grade 1. Ribociclib and everolimus may also be interrupted if symptoms are troublesome. If failure to recover to ≤Grade 1 within 3 weeks, subjects can resume ribociclib at full treatment dose (Table 6-5 and Table 6-6) until recovery to Grade ≤1. Once recovered, to Grade ≤1, reinitiate study treatment and reduce study treatment (ribociclib+everolimus+exemestane)by one dose level.
Grade 3 Symptomatic, interfering with ADL; O ₂ indicated	CT scan with lung windows and pulmonary function testing includes: spirometry, DLCO, and room air O ₂ saturation at rest. Repeat at least every 6 weeks until return to within normal limits. Bronchoscopy with biopsy and / or BAL is recommended.	Consider corticosteroids if infective origin is ruled out. Taper as medically indicated.	Hold study treatment until recovery to Grade ≤1. May restart study treatment within 3 weeks at a reduced dose (by one level) if evidence of clinical benefit.
Grade 4 Life threatening; ventilatory support	CT scan with lung windows and required pulmonary	Consider corticosteroids if infective origin is ruled out. Taper as	Discontinue study treatment

Worst Grade Pneumonitis	Required Investigations	Management of Pneumonitis	Dose Adjustment
indicated	function testing, if possible, includes: spirometry, DLCO, and room air O ₂ saturation at rest. Repeat at least every 6 weeks until return to within normal limits. Bronchoscopy with biopsy and / or BAL is recommended if possible.	medically indicated.	

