- Table 6-6: Updated to state: If toxicity recurs at grade 3: temporary dose interruption of ribociclib and everolimus until recovery to grade ≤ 1 and reduce to the next lower dose level, or continue at same dose with growth-factor support at the discretion of the treating investigator.
- Table 6-6: Modified to explain dose modifications if everolimus held more than 3 weeks.
- Section 10.1.5: updated to state “A subset of Full Analysis Set (FAS) excluding major protocol violations”.
- Section 10.4.1: Updated to reflect new statistical analysis plan for the phase II portion of the trial.
- Section 10.5.1: Updated to reflect new statistical analysis plan for the phase II portion of the trial.

Amendment 1

Amendment 1 rationale

Study CLEE011XUS29 (TRINITI-1) was initiated in June 2016. As of 4-Jan-17, a total of 18 Patients have been enrolled in the study.

The current amendment is intended to update the existing information about ribociclib, clarify specific aspects of the original protocol and remove inclusion criteria number 4 which required evaluation of total RB1. In addition the recommended phase II dose (RP2D) for this study has been determined to be 300mg Ribociclib (daily) + 2.5mg Everolimus (daily) + 25mg Exemestane (daily).

A summary of the key changes proposed in this amendment is listed below:

- Ribociclib information was updated based on the data available in the current IB version (v10, release date: Oct-10-2016; safety cut-off date: Jul-5-2016)
- Detailed information from the pivotal study CLEE011A2301 (MONALEESA-2) supporting the use of ribociclib + letrozole in aBC has been included to strengthen the study rationale.
- Remove inclusion criteria #4: Intact retinoblastoma protein (pRB). Confirmation of RB1status by IHC or an equivalent test required based on most recent tumor biopsy following progression on a CDK 4/6 inhibitor. If no tissue is available, most recent archival tissue should be tested for RB staining from metastatic site. This tissue sample should be tested locally for RB1 status.
 - After central evaluation of total RB1of patients enrolled into the phase I, dose escalation portion on the trial, it was determined by Novartis, and the Steering Committee that the inclusion criteria could be removed.

Amendment 01 also includes minor editorial changes and additional clarifications to address investigators' questions as described in the list of changes below.

Changes to the protocol

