6.4.1.1 Ribociclib (LEE011)

Management of severe or intolerable adverse reactions requires dose reduction, temporary interruption, and/or discontinuation of ribociclib therapy. Each patient is allowed a maximum of two dose reductions for ribociclib. After this, the patient will be discontinued from the study treatment. For each patient, once a dose level reduction for ribociclib has occurred, the dose level may be re-escalated during subsequent treatment cycles once discussed and approved by the sponsor. If a dose reduction is required, ribociclib should be reduced one dose level. Dose levels for ribociclib are provided in [Table 6-5](#).

A dose-dependent DDI was observed between ribociclib and everolimus based on clinical PK analyses in a separate dose escalation trial, where everolimus exposure increased 2- to 4-fold in the presence of ribociclib. If a dose adjustment of both ribociclib and everolimus are required, a dose reduction in ribociclib is considered as a method to reduce exposure to both drugs since everolimus exposure is increased with increased ribociclib doses through a DDI. After permanent discontinuation of either ribociclib, everolimus or exemestane, patients should be discontinued from study treatment. The dose modification guidelines for study treatment are found in [Table 6-5](#) and [Table 6-6](#).

Table 6-5 Phase I dose escalation (cohort A and B) and Phase II group 1: Dose modification guidelines for Ribociclib + everolimus + exemestane

	Ribociclib	Everolimus	Exemestane
	Dose	Dose	Dose
Starting dose	Phase I: refer to cohort A, or B. Phase II cohort 1: 300mg (daily)	2.5 mg daily	25 mg
First dose reduction	Reduced by 50mg	2.5 mg daily	
Second dose reduction	Change current dose to 21days out of 28	2.5 mg daily	

Table 6-6 Phase I dose de-escalation (cohort C) and Phase II cohort 2: Dose modification guidelines for Ribociclib + everolimus + exemestane

	Ribociclib	Everolimus	Exemestane
	Dose	Dose	Dose
Starting dose	200mg daily	If starting at dose level 0: 5mg daily	25 mg

		If starting at dose level -1: 2.5mg daily	
First dose reduction	200mg daily	If starting at dose level 0: 2.5mg daily If starting at dose level -1: 2.5mg every other day	
Second dose reduction	200mg daily	If starting at dose level 0: 2.5mg every other day If starting at dose level -1: discontinue from trial	

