Management of everolimus specific adverse reactions may require temporary dose reduction and/or interruption of everolimus therapy longer than 3 weeks. Recommendations for dose interruption of everolimus longer than 3 weeks in the management of everolimus specific adverse reactions are summarized in [Table 6-7](#). Clinical judgment of the treating physician should guide the management plan of each patient based on individual benefit/risk assessment ([USA Afinitor® PI 2012](#)).

Table 6-7 Dose modification guidelines for ribociclib (if everolimus is held longer than 3 weeks for pneumonitis)

	Ribociclib	Exemestane
	Dose	Dose
Starting dose	400 mg daily	25 mg
First dose reduction	200mg daily	
Second dose reduction	200mg 3 weeks on, 1 week off	

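### For Grade 2 pneumonitis unresolved after 3 weeks of interruption, Table 6-13 lets ribociclib resume at the assigned 200 to 300 mg, Table 6-7 starts it at 400 mg, and no sentence says which governs

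*Protocol*

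**What the plan says.** **Protocol 6.4.4.1, Table 6-13, Grade 2.** The default action is to reduce study treatment by one level. In addition, "Ribociclib and everolimus may also be interrupted if symptoms are troublesome". If the patient has not recovered to Grade 1 or better within 3 weeks, "subjects can resume ribociclib at full treatment dose (Table 6-5 and Table 6-6", and stays on that dose until recovery. The triplet restarts, one level lower, only after recovery.

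**Protocol 6.4.1.1, Tables 6-5 and 6-6.** For Group 1 the Table 6-5 starting dose reads "Phase II cohort 1: 300mg (daily". Cohorts A and B refer back to Table 6-2 (250 mg and 300 mg). Table 6-6 gives 200 mg daily for Cohort C and Group 2.

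**Protocol 6.4.1.1, Table 6-7.** The lead-in reads "Recommendations for dose interruption of everolimus longer than 3 weeks in the management of everolimus specific adverse reactions are summarized in" Table 6-7. The table is titled "Dose modification guidelines for ribociclib (if everolimus is held longer than 3 weeks for pneumonitis". It has columns for ribociclib and exemestane only. Ribociclib starts at 400 mg daily, drops to 200 mg daily, then to "200mg 3 weeks on, 1 week off". It names no pneumonitis grade and no dose group.

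**Protocol 7.2.2.6.1.** For a QTcF of 481 ms or more at any time after enrolment, the section requires sites to follow Table 6-7. QTcF management is in Table 6-9 (Protocol 6.4.3.2).

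**The concern.** The two tables address the same toxicity and the same 3-week threshold but name different ribociclib doses. A site that opens Table 6-13 finds the assigned dose; a site that opens Table 6-7 finds 400 mg, a dose assigned to no cohort or group in this trial. The gap is widest in Group 2 and Cohort C, the patients who start on everolimus 5 mg. What is at stake is consistent, unambiguous dosing during a drug-related lung toxicity.

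The QTcF cross-reference is a separate defect in the same set of rules. It sends sites, in mandatory terms, to a pneumonitis table that starts ribociclib at 400 mg, although Amendment 3 was written in part to require a ribociclib reduction at the first QTcF of 481 ms or more.

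**Working it through.** The plan states no figure to reproduce. The check is whether both tables reach the same patient, whether any text ranks them, and how far apart the doses are.

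**1. Do both tables apply?** In the Grade 2 interruption branch, Table 6-13 resumes ribociclib without everolimus and restarts the triplet only on recovery. If recovery has not come by 3 weeks, everolimus is off for longer than 3 weeks, which is the condition in the title of Table 6-7. That table has no grade limit, so it reaches this patient too.

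**2. What about the other grades?** Grade 1 continues at full dose and Grade 4 discontinues. For Grade 3, Table 6-13 holds study treatment until recovery and adds "May restart study treatment within 3 weeks at a reduced dose (by one level) if evidence of clinical benefit". It does not say what follows a longer Grade 3 hold. Table 6-7, read literally, would supply a ribociclib dose there. So the clear dose conflict is in Grade 2, and the scope of Table 6-7 for Grade 3 is unstated.

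**3. Does any text rank the tables?**
- The Table 6-7 lead-in sends long everolimus holds to that table but does not mention Table 6-13.
- Table 6-13 names Tables 6-5 and 6-6 and never Table 6-7.
- The appeal to clinical judgment in 6.4.1.1 gives discretion, not a dose.
- The 28-day hold rule in 6.4.1 governs discontinuation, not dose.

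**4. Size of the gap.** Inputs: assigned doses from Tables 6-2, 6-5 and 6-6; 400 mg and the 200 mg first reduction from Table 6-7.

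| Patients | Table 6-13 dose | Table 6-7 dose | Ratio | Difference |
|---|---|---|---|---|
| Group 1, Cohort B | 300 mg | 400 mg | 400/300 = 1.33 | 100 mg/day |
| Cohort A | 250 mg | 400 mg | 400/250 = 1.60 | 150 mg/day |
| Group 2, Cohort C | 200 mg | 400 mg | 400/200 = 2.00 | 200 mg/day |

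**5. Would replacing only the 400 mg entry work?** With the assigned dose as the start and 200 mg kept as the first reduction, the step is 300 − 200 = 100 mg (Group 1, Cohort B), 250 − 200 = 50 mg (Cohort A) and 200 − 200 = 0 mg (Group 2, Cohort C). In the last case the first reduction would be no reduction.

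**6. How often?** The documents give no rate for unresolved Grade 2 pneumonitis. Protocol 1.2.5.1.2 reports no pneumonitis among 16 evaluable patients in Cohorts A and B. The exact two-sided 95% upper limit for 0 of 16 is 1 − 0.025^(1/16) = 0.206, about 21%. Those patients took everolimus 2.5 mg, so the figure does not cover the 5 mg dose.

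**The case against.** The best case on the other side is that Table 6-7 is the more specific instruction and so already governs. It was written for this event, has no everolimus column, and its lead-in claims long everolimus holds. Its 200 mg first reduction makes sense for every group only if the start is above 200 mg. Ribociclib raises everolimus exposure, so a higher ribociclib dose with everolimus off is coherent, and continuous 400 mg was studied elsewhere (Protocol 1.2.1.4.3 and 2.1.1). On this view one pointer in Table 6-13 is incomplete and nothing more. The argument favours Table 6-7 but does not prove intent: Table 6-13 is specific to the same toxicity, the same threshold and the grade, and it names other tables.

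Two further objections stand in part. The wording is permissive in Table 6-13 and advisory in Table 6-7, so sites could differ, not necessarily would. The branch is also narrow: it needs optional interruption in place of the default reduction, and then no recovery by 3 weeks.

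On the QTcF pointer, the table titles should alert a careful reader. That reduces the practical risk but does not make a mandatory reference correct.

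A reader might also infer from the Amendment 2 list of changes that the Table 6-13 pointer is left over from renumbering. That list describes superseded text and uses the number 6-6 for more than one item, so it cannot settle the question.

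**Conclusion.** The protocol is wrong as written and should be corrected. In the Grade 2 branch described, two tables give ribociclib doses that differ by 100 to 200 mg a day, up to twofold, and nothing ranks them. This rests on reading the Table 6-13 full dose as the starting row of Tables 6-5 and 6-6, and on Table 6-7 having no grade limit, as its title and body show. The QTcF reference in 7.2.2.6.1 is a second, independent error.

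Three stronger readings are not supported:
- **That 400 mg is unsafe.** Protocol 2.1.1 describes acceptable tolerability of continuous 400 mg in other studies. In the nine patients on continuous 400 mg in Protocol 1.2.1.4.3 there was one dose-limiting toxicity, a Grade 3 AST elevation. This neither condemns the dose nor establishes it after pneumonitis.
- **That the trial's conclusion is affected.** Nothing shows an effect on the 24-week clinical benefit rate test.
- **That late recruitment makes the matter moot.** The SAP (section 4) counts 46 + 33 = 79 Phase II patients recruited so far, and Amendment 3 gives 79 as of a date. Neither says that recruitment had closed, and treatment continues until progression or intolerance.

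**What to change.** The sponsor first confirms the ribociclib dose intended while everolimus is off for pneumonitis.
- If it is 400 mg, point the Grade 2 row of Table 6-13 to Table 6-7 for that step.
- If it is the assigned dose, replace the 400 mg entry in Table 6-7 and revise its first-reduction row for Group 2 and Cohort C.

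In either case, state which pneumonitis grades Table 6-7 covers, given that Table 6-13 holds all study treatment for Grade 3 until recovery, and state that Tables 6-5 and 6-6 apply again once everolimus restarts. Separately, in 7.2.2.6.1 change the table reference for QTcF of 481 ms or more from Table 6-7 to Table 6-9.

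The cost is a clarification letter or a short amendment: one pointer or one or two table entries, a sentence or two on scope, and one corrected cross-reference. No new data or analysis is needed.

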6.4.5 Recommended actions to be taken for positive baseline hepatitis B test

Table 6-14 Recommendations for positive baseline hepatitis B test

Test	Result	Result	Result	Result	Result
HBV-DNA	+	+ or -	-	-	-
HBsAg	+ or -	+	-	-	-
HBs Ab	+ or -	+ or -	+ and no prior HBV vaccination	+ or -	- or + with prior HBV vaccination
HBc Ab	+ or -	+ or -	+ or -	+	-
Recommendation	Prophylaxis treatment should be started 1-2 weeks prior to first dose of study drug Monitor HBV-DNA approximately every 6 weeks			No prophylaxis Monitor HBV-DNA approximately every 4 weeks at the end of treatment and until EOT + 30 days	

Antiviral prophylaxis therapy should continue for at least 4 weeks after last dose of study drug. For hepatitis B reactivation, definition and management guidelines see [Table 6-15](#) Guidelines for management of hepatitis B.

Table 6-15 Guidelines for management of hepatitis B

Reactivation is Defined as:	Treatment
Increase of 1 log in HBV-DNA relative to baseline HBV- DNA value OR new	Start appropriate antiviral therapy AND Interrupt ribociclib and everolimus administration until resolution:

appearance of measurable HBV-DNA AND ALT elevation x 5 ULN	≤grade 1 ALT (or baseline ALT, if >grade 1) and ≤baseline HBV-DNA levels If resolution occurs within ≤21 days study treatment should be restarted at one dose lower, if applicable. If the patient is already receiving the lowest dose of study drug according to the protocol, the patient should restart at the same dose after resolution. Both antiviral therapies should continue at least 4 weeks after last dose of study drug. If resolution occurs >21 days Patients should discontinue study treatment but continue both antiviral therapies at least 4 weeks after last dose of study treatment
---	---

6.4.6 Guidance for all other adverse reactions

Consider performing an analysis of serum potassium, calcium, phosphorus, and magnesium for all adverse reactions, if indicated. If electrolyte values are outside of the normal range, interrupt ribociclib/everolimus administration, correct electrolytes with supplements or appropriate therapy as soon as possible, and repeat electrolyte testing until documented normalization of the electrolytes.

Table 6-16 Ribociclib/everolimus dose adjustment and management recommendation for all other adverse reactions

(see [Table 6-5](#) and [Table 6-6](#) for dose reduction guide)

Grade/Severity	Dose adjustment and management recommendations
Grade 1	No dose adjustment- maximize AE management
Grade 2	Dose interruption of ribociclib/everolimus until recovery to Grade ≤1 Initiate appropriate medical therapy and monitor Re-initiate study treatment at the same dose If the same toxicity recurs at Grade 2, interrupt ribociclib/everolimus until recovery to Grade ≤1. Re-initiate study treatment at the next lower dose level.
Grade 3	Hold both everolimus and ribociclib until it resolves to ≤Grade 1. Initiate appropriate medical management and monitor Re-initiate study treatment at the next lower dose level If toxicity recurs at grade 3, discontinue study treatment
Grade 4	Discontinue study treatment
Additional recommendations (see supplementary management brochure for further recommendations):	
Nausea: Ensure adequate hydration or fluid repletion. Consider performing an analysis of serum potassium, calcium, phosphorus and magnesium, if indicated. If electrolyte values are below LLN, interrupt ribociclib, correct electrolytes with supplements as soon as possible, and repeat electrolyte testing until documented normalization.	

Diarrhea: At the first sign of loose stools (Grade 1), initiate loperamide. Patient should remain well hydrated. Fluids and electrolytes should be replaced as needed. Consider performing an analysis of serum potassium, calcium, phosphorus and magnesium, if indicated. If electrolyte values are below LLN, interrupt ribociclib, correct electrolytes with supplements as soon as possible, and repeat electrolyte testing until documented normalization.

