AKI, acute kidney injury; EVE, everolimus; EXE, exemestane; GGT, gamma-glutamyltransferase. ^a Includes neutropenia, neutrophil count decreased, and white blood cell count decreased. ^bIncludes thrombocytopenia and platelet count decreased.

2 Rationale

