***Note: Phase I does not require prior CDK 4/6 inhibitor exposure**

***Note: For patients who received prior CDK4/6 inhibition as part of a clinical trial, patients must be unblinded in order to verify that the patient did receive a CDK4/6 inhibitor.**

10. ECOG Performance Status 0 – 1.
11. Radiological evidence of recurrence or progression on or after the last therapy prior to starting study treatment.
12. Patients must have:
 - Measurable disease (based on RECIST 1.1): defined as at least one lesion that can be accurately measured in at least one dimension ≥ 20 mm with conventional imaging techniques or ≥ 10 mm with spiral CT or MRI,
OR
 - Evaluable disease: bone lesions- lytic or mixed (lytic + sclerotic) in the absence of measurable disease
13. Patient has adequate bone marrow and organ function as defined by the following LOCAL laboratory values at screening:

- Absolute neutrophil count $\geq 1.5 \times 10^9/L$.
 - Platelets $\geq 100 \times 10^9/L$.
 - Hemoglobin $\geq 9.0 \text{ g/dL}$.
 - Potassium, total calcium (corrected for serum albumin), magnesium and sodium within normal limits for the institution or corrected to within normal limits with supplements before first dose of study medication.
 - INR ≤ 1.5 or ≤ 2.5 while on anti-coagulant.
 - Estimated glomerular filtration rate (eGFR) $\geq 30 \text{ mL/min/1.73m}^2$ according to the Modification of Diet in Renal Disease (MDRD) formula
 - Serum creatinine $< 1.5 \text{ mg/dL}$ or creatinine clearance $\geq 50 \text{ mL/min}$.
 - Total bilirubin $< \text{ULN}$ except for patients with Gilbert's syndrome who may only be included if the total bilirubin is $\leq 3.0 \times \text{ULN}$ or direct bilirubin $\leq 1.5 \times \text{ULN}$.
 - Alanine aminotransferase (ALT) and aspartate transaminase (AST) $< 2.5 \times \text{ULN}$, except for patients with liver metastasis, who are only included if the AST is $< 5 \times \text{ULN}$.
14. Must be able to swallow ribociclib, everolimus and exemestane capsules/tablets.
15. Patients with metastatic disease are allowed to receive ≤ 28 days of endocrine therapy prior to starting study treatment.

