5.3 Exclusion criteria

Patients eligible for this study must not meet any of the following criteria:

1. Patient with visceral crisis or any disease burden that makes the patient ineligible for this study per the investigator's best judgment.
2. Patients who received more than one line of chemotherapy for advanced breast cancer.

****Note: A chemotherapy line in advanced disease is an anticancer regimen(s) that contains at least 1 cytotoxic chemotherapy agent and given for greater 21 days or longer. If a cytotoxic chemotherapy regimen was discontinued for a reason other than disease progression and lasted 21 days or less, then this regimen does not count as a "prior line of chemotherapy"***

3. HER2 overexpression by local laboratory testing (IHC 3+ staining or *in situ* hybridization positive).
4. Patient has received prior treatment with anthracyclines at cumulative doses of 450 mg/m^2 or more for doxorubicin or 900 mg/m^2 or more for epirubicin.
5. Patient with a known hypersensitivity to any of the excipients of ribociclib, mTOR inhibitors, e.g. sirolimus (rapamycin), exemestane.
6. Previous treatment with mTOR inhibitors.
7. Previous treatment with exemestane for metastatic disease (except patients who received ≤ 28 days of exemestane for advanced breast cancer and did not progress).

8. Disease progression on more than one CDK 4/6 inhibitor, or have progressed more than once on the same CDK 4/6 inhibitor.
9. Patient is concurrently using other anti-cancer therapy. All anti-cancer therapy must be discontinued atleast 7 days to study treatment (C1D1). Drugs with overlapping toxicities with either everolimus or ribociclib must also be discontinued at least 7 days prior to C1D1. All AEs related to prior treatment should have resolved to CTCAE version 4.03 Grade ≤ 1 prior to study treatment (including any CDK 4/6 inhibitor).".
10. Patient has not recovered from all toxicities related to prior anticancer therapies to Grade ≤ 1 (based on NCI CTCAE version 4.03). Exception to this criterion: patients with any grade of alopecia and or neuropathy are allowed to enter the study.
11. Patient has had major surgery within 14 days prior to starting study drug or has not recovered from major side effects.
12. Patients with Child Pugh score B or C.

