6.4 Dose modification

6.4.1 Dose cohort modification

For patients who do not tolerate the protocol-specified dosing schedule, ribociclib adjustments are **recommended** in order to allow the patient to continue the study treatment.

Dose reductions are not permitted for everolimus, exemestane or GnRH agonists (if patient is currently taking). Any changes to the dose or interruption of dosing must be recorded on the Dosage Administration Record eCRF. Patients who require a study treatment hold of more than 28 days will be discontinued from the study unless discussed and approved by the sponsor ([Section 7.1.2](#)). Once dose-reduced the dose may be re-escalated once discussed and approved by the sponsor. All patients will be followed for AEs and for SAEs for 30 days following the last dose of study drug.

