		level. Maintain everolimus at same dose
Febrile Neutropenia	Grade 3: ANC<1.0 x 10 ⁹ /L with [a single temperature of >38.3 degrees C (101 degrees F) or a sustained temperature of >=38 degrees C (100.4 degrees F) for more than one hour] .	Dose interruption of both ribociclib and everolimus until improvement of ANC \geq 1.0 x 10 ⁹ /L and no fever. Restart at the next lower dose level. If febrile neutropenia recurs, discontinue study treatment. Colony Stimulating Factors should be considered in patients with fever and profound neutropenia (<1.0 x 10 ⁹ /L)
	Grade 4 Life-threatening consequences; urgent intervention indicated	Discontinue study treatment
Anemia (Hemoglobin)	Grade 1: \geq 10.0 – LLN g/dL	No dose adjustment required
	Grade 2: \geq 8.0 – <10.0 g/dL	No dose adjustment required.
	Grade 3: <8.0 g/dL	Dose interruption of ribociclib and everolimus recovery to grade 1. Re-initiate study treatment at the same dose.
	Grade 4: Life-threatening consequences; urgent intervention indicated	Discontinue study treatment PRBC transfusion to be considered per NCCN guidelines

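### Leukopenia and lymphopenia fall to Table 6-16 and get stricter actions than neutropenia of the same grade in Table 6-8, and the anemia restart level lies above the entry level

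*Protocol*

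**What the plan says.** **White cells.** Protocol section 6.4.3.1 (Table 6-8) has rows for thrombocytopenia, neutropenia, febrile neutropenia and anemia only. No dose-modification table names leukopenia, white blood cell decrease or lymphopenia, so these go to Table 6-16 in section 6.4.6, the table for all other adverse reactions. Its Grade 2 rule is "Dose interruption of ribociclib/everolimus until recovery to Grade ≤1". For Grade 3 it holds and restarts one level lower, then says "If toxicity recurs at grade 3, discontinue study treatment". Grade 4 is discontinued. In section 1.2.5.1.2, the footnote to the neutropenia row of Table 1-7 reads "Includes neutropenia, neutrophil count decreased, and white blood cell count decreased", while leukopenia and lymphopenia have rows of their own in that table.

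**Anemia.** Table 6-8 makes no adjustment at Grade 2 (8.0 to below 10.0 g/dL). At Grade 3 (below 8.0) the instruction is "Dose interruption of ribociclib and everolimus recovery to grade 1", with restart at the same dose. Grade 1 begins at 10.0 g/dL. Inclusion criterion 13 in section 5.2 admits patients at 9.0 g/dL or more. Section 6.4.1 says "Patients who require a study treatment hold of more than 28 days will be discontinued from the study", and the same sentence lets the sponsor approve otherwise.

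**Alopecia.** Exclusion 10 in section 5.3 asks that prior-therapy toxicity be Grade 1 or better, with the exception that "patients with any grade of alopecia and or neuropathy are allowed to enter the study". Table 6-16 has no similar exception.

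**The concern.** The hematology panel in Table 7-4 is a white cell count with differential, so neutrophils, lymphocytes and total white cells are reported together, and neutrophils are part of the total. Two investigators looking at similar results may report different terms. If one term leads to Table 6-8 and the other to Table 6-16, patients in the same state receive different exposure, and some are stopped while others continue.

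The anemia row raises a separate difficulty. A patient whose admissible hemoglobin at entry was 9.0 to 9.9 g/dL, and who later has a Grade 3 fall, must rise above her own starting value before she may resume.

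Both matter for dose intensity, for tolerability summaries (interruptions, reductions and their reasons) and for discontinuations that the wording causes rather than a clinical decision.

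**Working it through.** The plan gives no figure to reproduce here. The check sets the rules side by side.

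**Step 1. White cells, by grade (Tables 6-8 and 6-16).**

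| Grade | Neutropenia, Table 6-8 | Leukopenia or lymphopenia, Table 6-16 |
|---|---|---|
| 2 | No change | Hold to Grade 1 or better; same dose, one level lower if it recurs |
| 3, first | Hold to ANC 1.0 × 10⁹/L; same dose | Hold to Grade 1 or better; one level lower |
| 3, recurrent | Hold and reduce, or same dose with growth factor | Discontinue |
| 4 | Hold to ANC 1.0 × 10⁹/L; ribociclib one level lower | Discontinue |

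The actions differ in every row. In the last two rows the difference is between staying on treatment and leaving it.

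**Step 2. Does the adverse event definition settle which table applies?** Section 8.1.1 makes a laboratory value an adverse event only if it is symptomatic, clinically significant, or needs therapy or a change in study medication. Section 8.1.2.1 adds that an abnormality for which the protocol requires a hold is an adverse event by definition. Whether a hold is required depends on the table, and whether the table applies depends on the event. The definition is circular on this point.

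**Step 3. Hemoglobin (Table 6-8 and inclusion 13).**

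| g/dL | Grade | Meets entry limit | No earlier Grade 3 | Recovering from Grade 3 |
|---|---|---|---|---|
| 7.9 | 3 | No | Hold | Hold |
| 8.0–8.9 | 2 | No | Continue | Hold |
| 9.0–9.9 | 2 | Yes | Continue | Hold |
| 10.0 | 1 | Yes | Continue | Restart |

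The restart level is 10.0 − 9.0 = 1.0 g/dL above the entry limit and 10.0 − 8.0 = 2.0 g/dL above the lowest value at which treatment continues. Elsewhere the protocol does allow for baseline: Table 6-11 uses recovery to baseline for ALT and AST, and Table 6-15 accepts baseline ALT where that was above Grade 1. The anemia row and Table 6-16 have no such clause.

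**Step 4. How often could this arise?** Table 1-6 (N=77) gives all grades and Grade 3/4, but not Grade 2. The share at Grade 2 or above can only be bounded, between the Grade 3/4 count and the all-grade count:

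- White cell decrease: 9/77 = 11.7% to 25/77 = 32.5%
- Lymphopenia: 5/77 = 6.5% to 14/77 = 18.2%
- Lymphocyte count decreased: 3/77 = 3.9% to 13/77 = 16.9%
- Anemia, Grade 3/4: 5/77 = 6.5%

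These rows may share patients and must not be added. They come from a study that gave ribociclib three weeks on and one week off. In this trial's Phase I (Table 1-7, n=16), leukopenia and lymphopenia were each 1/16 = 6.3%, and Grade 3/4 anemia was 2/16 = 12.5%. White cell decrease is not shown separately there because it is counted within neutropenia.

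**The case against.** Several points on the other side are sound.

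- **Anemia.** Restarting at a stricter level than the one that triggers a hold can be deliberate. A reader might infer that two rules collide at 9.5 g/dL. They do not, because the action depends on whether Grade 3 occurred earlier. Inclusion 8 and exclusion 10 also keep out patients whose Grade 2 anemia is a toxicity of prior therapy, which narrows the group entering at 9.0 to 9.9. Discontinuation after 28 days is not automatic, since the sponsor may approve a longer hold. What stands is that the restart level ignores an admissible low baseline.
- **White cells.** A reader might infer that one blood count is shown to trigger opposite actions at once. The documents print no white cell or lymphocyte grade cut-offs, so numerical overlap cannot be shown; the conflict is by grade. Section 8.1.2.1 prefers a diagnosis and does not require a result corresponding to a sign or symptom of an already reported event to be recorded again. The Table 1-7 footnote points towards treating white cell decrease as neutropenia. Neither of these is carried into Table 6-8 or 6-16, and neither covers lymphopenia or isolated leukopenia.
- **Alopecia.** The entry exception concerns prior-therapy toxicity, not a new on-study reaction, so this is a missing counterpart and not a contradiction.
- **Frequency.** Table 1-7 does not support calling leukopenia or lymphopenia frequent in this trial. Some white cell events will accompany neutropenia that would be held anyway.

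**Conclusion.** The point holds as a conflict of wording with practical consequences. For leukopenia, white cell decrease and lymphopenia, the default to Table 6-16 gives a stricter action than neutropenia receives at Grade 2, at Grade 3 (first and recurrent) and at Grade 4. The reported term can therefore decide between continuing and stopping. The anemia restart level is 1.0 g/dL above the entry level with no baseline allowance. The alopecia gap is minor.

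The size is only loosely known. The ranges above are upper limits on those affected, because the documents do not separate Grade 2 events, events without neutropenia, or patients who entered below 10.0 g/dL. The conclusion assumes that a reaction with no row of its own follows Table 6-16, and that the supplementary management brochure cited there, which is not among the documents, does not say otherwise.

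A reader might go on to infer lost Week 24 benefit or lost power. The documents do not support that. Patients who stop for reasons other than progression keep 8-weekly scans (Protocol 4.1.3 and 7.1.7). SAP section 3.5.2.2 counts response or stable disease in the first 24 weeks without progression, so a toxicity stop is not in itself a clinical benefit failure. Nothing in the documents links these holds to a change in the clinical benefit rate. The effect is on consistency of exposure, dose intensity and avoidable discontinuation.

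**What to change.** Reconcile inclusion 13, exclusion 10, Table 6-8 and Table 6-16:

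1. State in both tables which one governs leukopenia or white cell decrease and lymphopenia, when each occurs alone and when it occurs with neutropenia.
2. Make the anemia restart, stay-on and entry levels compatible, and say what applies to patients whose baseline is below 10.0 g/dL.
3. State whether Table 6-16 has any alopecia exception.

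The levels and actions are for the sponsor's clinicians to set; the request is only that the passages agree.

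The cost is table wording in a protocol amendment, with no new assessments. SAP section 4 records 46 and 33 patients already recruited to the two Phase II groups, so new wording helps only those still on treatment. For the rest, a listing of holds, reductions and discontinuations for white cell, lymphocyte and anemia events, showing the reported term and the action taken, would reveal how sites applied the tables. The dosing and adverse event data for it are already collected.
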